### **7.1.2.1 Adverse Event (AE) Monitoring**

The investigator or qualified designee will assess each subject to evaluate for potential new or worsening AEs as specified in the Trial Flow Chart (Section 6.0) and more frequently if clinically indicated. Adverse experiences will be graded and recorded throughout the study and during the follow-up period according to NCI CTCAE Version 4.0 (see Section 11.2). Toxicities will be characterized in terms regarding seriousness, causality, toxicity grading, and action taken with regard to trial treatment.

Please refer to section 7.2 for detailed information regarding the assessment and recording of AEs.

### **7.1.2.2 Full Physical Exam**

The investigator or qualified designee will perform a complete physical exam during the screening period. Clinically significant abnormal findings should be recorded as medical history. A full physical exam should be performed during screening.

### **7.1.2.3 Vital Signs**

The investigator or qualified designee will take vital signs at screening, prior to the administration of each dose of trial treatment and at treatment discontinuation as specified in the Trial Flow Chart (Section 6.0). Vital signs should include temperature, pulse, respiratory rate, weight and blood pressure. Height will be measured at screening only.

### **7.1.2.4 Eastern Cooperative Oncology Group (ECOG) Performance Scale**

The investigator or qualified designee will assess ECOG status (see Section 11.1) at screening, prior to the administration of each dose of trial treatment and discontinuation of trial treatment as specified in the Trial Flow Chart (Section 6.0).

### **7.1.2.5 Tumor Imaging and Assessment of Disease**

All tumor assessments will be performed according to the Trial Flow Chart (Section 6.0). If a patient discontinues treatment for any reason other than progression, tumor assessments will be done every 12 weeks ( $\pm$  14 days) for duration of study disease monitoring of 24 months unless after cycle 8 in which case they will be performed every 16 weeks ( $\pm$  14 days).

#### **7.1.2.5.1 Methods of Tumor Assessment**

The preferred imaging modality is CT scan. Other modalities (MRI, PET-CT, ultrasound, endoscopy, laparoscopy, cytology, histology) may be used as adjuncts. If there is a compelling reason to do PET/CT scans or MRI (e.g. patient has allergy to iodinated contrast), the PI should

be contacted for permission.

All measurements should be taken and recorded in metric notation using a ruler or calipers. The same method of assessment and the same technique must be used to characterize each identified and reported lesion at baseline and during follow-up. Imaging-based evaluation is preferred to evaluation by clinical examination unless the lesion(s) being followed cannot be imaged but are assessable by clinical exam. Combinations of clinically measurable and radiographically measurable are permissible. For example, the patient may have dermal lesions that are most accurately measured by clinical evaluation with a ruler or calipers, and lymph nodes that are most accurately measured on CT scan.

Cytology and histology may be helpful to differentiate a complete response from a partial response.

#### **7.1.2.5.2 RECIST version 1.1**

The primary set of response criteria for this trial is RECIST v1.1. See Appendix 11.3 for criteria for complete response (CR), partial response (PR), stable disease (SD), and progressive disease (PD).

RECIST v1.1 will be modified for this trial. To account for tumor pseudo-progression that can sometimes occur with immunotherapy, it is required that RECIST PD be confirmed on a subsequent assessment performed 4-6 weeks later (see Section 7.1.2.5.4 for details).

#### **7.1.2.5.3 Evaluation of Best Overall Response (BOR)**

The best overall response is the best response (Target + non-target lesions) recorded from the start of the treatment until disease progression/recurrence or non-protocol therapy (taking as reference for progressive disease the smallest measurements recorded since the treatment started). The patient's best response assignment will depend on the achievement of both measurement and confirmation criteria.

#### **7.1.2.5.4 Confirmation of PD**

iRECIST is based on RECIST 1.1, but adapted to account for the unique tumor response seen with immunotherapeutic drugs. iRECIST will be used by the investigator to assess tumor response and progression and make treatment decisions. When clinically stable, participants should not be discontinued until progression is confirmed per iRECIST. Allowing patients to continue treatment despite the initial radiologic progression takes into account the observation that some patients can have a transient tumor flare in the first few months after start of immunotherapy with subsequent disease response. The minimal criteria must be met to continue treatment in patients with radiological PD. Such criteria may include the following:

1. No symptoms or signs (including worsening of laboratory values) indicating disease progression
2. No decline in ECOG performance status or symptomatic clinical deterioration

3. No evidence of rapid progression of disease or of progressive tumor at critical anatomical sites (e.g., cord compression) requiring urgent alternative medical intervention

If a patient does not meet all of the requirements above, the patient should be removed from trial immediately for unconfirmed PD with clinical demise. Every effort should be made to document the objective progression even after discontinuation of treatment. Patients with a global deterioration of health status requiring discontinuation of treatment without objective evidence of disease progression at that time (not evaluated by confirmatory scan) should be reported as “symptomatic clinical deterioration.”

For patients who are clinically well and meet the criteria above, the patient may remain on treatment at the discretion of the investigator, and imaging should be repeated no less than 4 weeks but no more than 6 weeks later (4-6 weeks). If repeat imaging does not confirm PD per iRECIST (below), as assessed by the Investigator, and the participant continues to be clinically stable, study treatment may continue and follow the regular imaging schedule.

If the repeat assessment shows demonstrates PD (relative to baseline or the nadir tumor burden, whichever is smaller) as per iRECIST criteria below, treatment will be discontinued. The development of confirmed PD and/or the development of symptomatic clinical deterioration constitutes confirmed progressive disease. In the case of confirmed progressive disease, study treatment should be discontinued.

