#### **7.1.2.5.6 Determining the date of progression or response**

For all patients who experience disease progression on study, the date noted for disease progression is the time of the scan when it was originally determined, and not the later date of the confirmatory scan.

For all patients who experience complete or partial response on study, the date noted for disease response is the time of the scan when it was originally determined, and not the later date of the confirmatory scan.

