#### **7.1.5.4.1 Survival Follow-up**

Once a subject experiences confirmed disease progression or starts a new anti-cancer therapy, the subject moves into the survival follow-up phase and should be contacted by telephone every 12 weeks to assess for survival status until death, withdrawal of consent, or the end of the study, whichever occurs first. During the survival follow-up, the following conditions will be assessed for each patient: survival status and any new cancer therapy received.

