## 8.0 STATISTICAL ANALYSIS PLAN

Sample size justification. To address the primary objective, we have calculated the 95% confidence intervals (CI's) to assess precision of expected response rate of pembrolizumab in treating patients with specified mutant tumors (e.g., *POLE*, *POLD1*, and *BRCA1* and 2). Responses to single agent PD-1 inhibition are not seen in the majority of patients; available published data in pretreated triple negative breast, lung, ovarian tumors, histologies likely to be enrolled to this trial, have ranged from 11-19% in small studies. Based on the data in MSI high tumors by Le et al, responses can be expected to rise significantly in tumors with genomic instability, with the lowest rate of 40% in their published series. We thus assume that the response rate of pembrolizumab in our trial, treating patients with *POLE* (or *POLD1*) and/or *BRCA1/2* mutant tumors, will similarly be at about 40%. For n=23 patients for each type of tumors ([*POLE* or *POLD1*] and [*BRCA1* and 2]), we expect to yield a 95% CI of (0.20, 0.60), within the 40%+/- 20% range (Table 7). This confidence interval is above the response rate of using standard therapy in treating unselected cancer patients suggesting significant improvement of pembrolizumab over standard therapies.

To address the secondary objective, we used the same 95% CI calculations (Table 7), assuming no loss of follow-up, to assess the precision of expected PFS rate of pembrolizumab at 6 months in treating patients with specified mutant. Based on the data in Le et al (Panel C Fig 2), the PFS rate at 6 months was at least 35% while the immune-related PFS at 20 weeks was at least 67%. Assuming the 6-month PFS rates in our study will be similarly at least 35%. With n=23 patients for each type of tumors ([*POLE* or *POLD1*] and [*BRCA1* and 2]), we expect to yield a 95% CI of (0.15,0.55) for PSF of 35% and (0.46,0.84) for PSF of 65%, both within the +/- 20% range.

**Table 7. 95% Confidence Intervals for Response and/or PFS\* Rate Based on Estimated Rate (P) and Sample Size (n) for a Specific Mutant Tumor.**

P							
n	0.25	0.30	0.35	0.40	0.50	0.65	0.75
20	(0.06,0.44)	(0.10,0.50)	(0.14,0.56)	(0.18,0.62)	(0.28,0.72)	(0.44,0.86)	(0.56,0.94)
23	(0.07,0.43)	(0.11,0.49)	(0.15,0.55)	(0.20,0.60)	(0.29,0.71)	(0.46,0.84 )	(0.57,0.93)

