25	(0.08,0.42)	(0.12,0.48)	(0.16,0.54)	(0.20,0.60)	(0.30,0.70)	(0.46,0.82 )	(0.58,0.92)
26	(0.08,0.42)	(0.12,0.48)	(0.16,0.54)	(0.21,0.59)	(0.30,0.70)	(0.48,0.82 )	(0.59,0.91)

28	(0.09,0.4)	(0.13,0.47)	(0.17,0.53)	(0.21,0.59)	(0.31,0.69)	(0.47,0.83 )	(0.59,0.91)
30	(0.10,0.40)	(0.13,0.47)	(0.18,0.52)	(0.22,0.58)	(0.32,0.68)	(0.48,0.82 )	(0.60,0.90)
*CI calculations for PFS assumed no loss of follow-up.							

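### Symptomatic clinical deterioration counts as confirmed progression, but progression is dated only by a scan, so a deterioration with no progressive scan has no date, or a late one, in the secondary 6-month PFS rate

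*Combined protocol and SAP*

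**What the plan says.** All references are to the combined protocol and SAP.

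- **What counts as progression.** Section 7.1.2.5.4: "The development of confirmed PD and/or the development of symptomatic clinical deterioration constitutes confirmed progressive disease". The label is for patients whose general decline forces them off treatment "without objective evidence of disease progression at that time (not evaluated by confirmatory scan". The same section asks sites to try to document objective progression after treatment stops.
- **How progression is dated.** Section 7.1.2.5.6: "For all patients who experience disease progression on study, the date noted for disease progression is the time of the scan" that first showed it, not the confirmatory scan. No other dating rule is given.
- **What follows progression.** Section 7.1.5.4.1: "Once a subject experiences confirmed disease progression or starts a new anti-cancer therapy, the subject moves into the survival follow-up phase", with telephone contact every 12 weeks. Section 5.6 also prescribes telephone follow-up, once progression is documented.
- **Imaging at and after discontinuation.** The flow chart in Section 6.1 marks tumor imaging at the discontinuation visit, and its footnote 5 continues imaging until progression. Section 7.1.4 asks for the final-visit activities at discontinuation. The list of discontinuation assessments in Section 7.1.5.3 does not include imaging.
- **How PFS is used.** Section 8.0 plans a 6-month PFS rate for the secondary objective as a simple proportion of 23 patients per cohort. The footnote to Table 7 says: "CI calculations for PFS assumed no loss of follow-up". The text reviewed has no list of PFS events, no role for death, no censoring rule and no estimator.

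**The concern.** One section creates a progression event that needs no scan. Another dates every progression by a scan. When a patient deteriorates and no scan has shown progression, the protocol declares an event that its own rule cannot date. If a later scan does show progression, the rule gives that scan's date, although the patient already counted as progressed.

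These patients are likely to be among those who do worst. Dropping them, censoring them at their last scan or dating them to a late scan would each raise the 6-month PFS rate without any real benefit if the deterioration came before 6 months. That rate is to be set against historical data from unselected patients (Section 3.2), with no control arm. If the choice is left until the data are in hand, it will be made in an open-label trial with outcomes known.

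**Working it through.** **1. The plan's own figure.** Inputs from Section 8.0: n = 23 per cohort and a 6-month PFS rate of 0.35. The Wald interval is p ± 1.96 × √(p(1 − p)/n).

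0.35 ± 1.96 × √(0.35 × 0.65/23) = 0.35 ± 0.195 = (0.155, 0.545)

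The plan gives (0.15, 0.55), so it reproduces to within 0.01. The calculation treats the 6-month status of all 23 patients as known.

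**2. Scan times.** Footnote 3 to the flow chart places scans before Cycles 4, 7 and 11, in 3-week cycles: 3 × 3 = week 9, 6 × 3 = week 18 and 10 × 3 = week 30. Taking 6 months as week 26, no routine scan falls between week 18 and the landmark.

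**3. Three records under the two rules.**

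| Record | Event under 7.1.2.5.4 | Date under 7.1.2.5.6 |
|---|---|---|
| Progressive scan at week 9, deterioration at week 11 | Yes | Week 9, correct |
| Stable at week 9, deterioration at week 14, no progressive scan | Yes | None |
| As above, but a scan at week 30 shows progression | Yes, at week 14 | Week 30, so progression-free at week 26 |

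The last two records require that the discontinuation scan was not done or did not show progression.

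**4. Effect on the rate.** Start from 8 of 23 progression-free at 6 months (23 × 0.35 = 8.05), which is 34.8%. Let k be the number of deteriorations before week 26 with no progressive scan by then. The documents do not give k; 1 to 3 is an assumption, and 3 is 20% of the 15 progressions.

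| k | Dropped: 8/(23 − k) | Kaplan-Meier, censored at last scan | Dated after week 26: (8 + k)/23 |
|---|---|---|---|
| 1 | 8/22 = 36.4% | 36.4–37.9% | 9/23 = 39.1% |
| 2 | 8/21 = 38.1% | 38.1–41.7% | 10/23 = 43.5% |
| 3 | 8/20 = 40.0% | 40.0–46.4% | 11/23 = 47.8% |

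The lower Kaplan-Meier figures apply if the deterioration precedes week 9: with no scan after baseline, censoring at the last scan equals dropping. The upper figures assume 11 progressions by week 9 and 4 in weeks 9–18, with the k deteriorations among those 4 and censored at week 9: 12/23 × 8/(12 − k). For k = 1 this is 12/23 × 8/11 = 37.9%.

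**5. Direction.** The shift is not always upward. Dropping one patient who deteriorates after 6 months gives 7/22 = 31.8%.

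**The case against.** The strongest reply is that Section 7.1.2.5.4 concerns confirmation of a progression already seen on a scan. Its bracketed reference to a confirmatory scan presupposes a first one, and its criteria are for patients with radiological progression. On that reading deterioration stands in for the second scan, and the first scan supplies a correct date. This holds for many of these patients. It does not cover everyone the wording admits, because the label also fits a patient with no objective evidence of progression at all.

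Next, the protocol asks for imaging at and after discontinuation. A discontinuation scan that shows progression does date the event at about the right time. One that is missed or shows stable disease does not. Footnote 5 stops imaging at progression, which Section 7.1.2.5.4 says has already happened, and Section 7.1.5.4.1 then moves the patient to telephone contact. Section 5.6 ties telephone contact to documented progression, which such a deterioration arguably is not. So a reader cannot say that these patients simply go unimaged; the texts conflict.

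A reader might also infer that every symptomatic deterioration is undated and that the 6-month PFS rate is therefore overstated. The documents do not support that. Patients with an earlier progressive scan are dated correctly, and nothing in the plan says the others will be dropped, censored or dated late.

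Finally, in an open-label trial using RECIST 1.1, PFS based on scans and deaths only is a defensible main analysis. That is fair, but the plan does not choose it, and its present wording counts the deterioration.

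**Conclusion.** The defect is real and narrow. The protocol counts deterioration as confirmed progression, and its only dating rule gives no date, or a late one, when no earlier scan showed progression. For the same patients the imaging provisions and the telephone route disagree and must be reconciled.

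If such a deterioration occurs before 6 months, one patient of 23 raises the PFS rate by about 2 points when dropped (36.4 − 34.8 = 1.6) and about 4 points when dated late (39.1 − 34.8 = 4.3). Both shifts are small beside the planned interval of roughly ± 20 points, but several such patients would matter. The size rests on an assumed count. It would be smaller if death is a PFS event, because survival follow-up would then capture some of these patients as events before week 26. The endpoint is secondary and the primary response rate is unaffected. This should be corrected before analysis.

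**What to change.** In Section 7.1.2.5.6, add: Where progression is by symptomatic clinical deterioration and no earlier scan showed progression, the progression date is the day the deterioration is recorded, whether or not a later scan shows progression. Where an earlier scan showed progression, that scan's date stands.

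In Section 8.0:

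- Estimate 6-month PFS by Kaplan-Meier with a log-log 95% confidence interval, in place of a proportion that assumes no loss to follow-up.
- Name the events: scan-dated progression, dated clinical deterioration, and death.
- State how patients who start new anti-cancer therapy before progression are handled. Section 7.1.5.4.1 moves them to survival follow-up as well, and censoring them may be informative.
- Add a sensitivity analysis with radiographic progression or death as the only events.

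Reconcile Sections 5.6, 6.1 (footnote 5), 7.1.2.5.4, 7.1.4, 7.1.5.3 and 7.1.5.4.1 on imaging and follow-up for these patients.

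The cost is a few sentences and, if the case report form lacks one, a date field for the deterioration. The downside is that a few investigator-judged events enter PFS in an open-label trial and the reported rate may be slightly lower. The sensitivity analysis shows how much depends on them.

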#### Confirmation of Progression per iRECIST

Progression is considered confirmed, and the overall response will be confirmed progressive disease per iRECIST (iCPD), if ANY of the following occurs:

- Any of the factors that were the basis for the initial unconfirmed progressive disease (iUPD) show worsening
  - For target lesions, worsening is a further increase in the sum of diameters of  $\geq 5$  mm, compared to any prior iUPD time point
  - For non-target lesions, worsening is any significant growth in lesions overall, compared to a prior iUPD time point; this does not have to meet the “unequivocal” standard of RECIST 1.1
  - For new lesions, worsening is any of these:
    - An increase in the new lesion sum of diameters by  $\geq 5$  mm from a prior iUPD time point
    - Visible growth of new non-target lesions
    - The appearance of additional new lesions
- Any new factor appears that would have triggered PD by RECIST 1.1

#### **7.1.2.5.5 Confirmation of PR or CR**

The subject's first instance of a PR or CR should be confirmed on a repeat assessment no less than 4 weeks later (4-6 weeks); however, it is acceptable to delay the repeat assessment until the next scheduled interval imaging study (12 weeks  $\pm$  7 days) at the discretion of the treating investigator, or if the patient prefers not to have an extra CT scan for this purpose. A biopsy of any residual lesion may be used to confirm a CR at the discretion of the treating investigators.

#### **7.1.2.5.6 Determining the date of progression or response**

For all patients who experience disease progression on study, the date noted for disease progression is the time of the scan when it was originally determined, and not the later date of the confirmatory scan.

For all patients who experience complete or partial response on study, the date noted for disease response is the time of the scan when it was originally determined, and not the later date of the confirmatory scan.

#### **7.1.2.6 Tumor Tissue Collection and Correlative Studies Blood Sampling**

##### **7.1.2.6.1 Genomics/Sequencing:**

In collaboration with [name], PhD, Director of the Functional Genomics Shared Resource, we propose to perform genomic sequencing analysis of pre-treatment biopsy specimens, and specimens, if available at progression. Next generation DNA sequencing of exomes will commence, and RNA sequencing will evaluate selected gene expression. Tumor samples, and where available, matched normal tissue or peripheral blood lymphocytes, will be assayed by whole exome sequencing to determine the set and amount of genomic variants present. In addition to standard variant analysis, we will also implement algorithm such as NAsEEK to look for presence of immunogenic neo- antigens. For cancer specimens from *BRCA1/2* mutation carriers, where there is likely a high burden of genomic rearrangements, we will also look for presence of gene fusion using the NUGEN SPET approach. *BRCA1/2* mutant specimens will also be analyzed by CGH to assay for specific patterns of gross genomic alterations (allelic imbalance, large scale transitions, etc). By this approach we hope to determine if the nature and/or pattern of genomic changes present, as well as the presence of potential immunogenic neoantigens, will correlate with response to pembrolizumab.

##### **7.1.2.6.2 Tissue/Blood:**

In collaboration with [name], Managing Director of the Immune Monitoring Core, we propose to assess the frequencies, activation/differentiation, functionality, and co-inhibitory molecule expression of immune cell populations in peripheral blood and tumor, before and after treatment with systemic pembrolizumab. We will measure the following immunologic parameters that may be indicative of responsiveness to treatment using advanced multi-parameter flow cytometric approaches and immunohistochemistry:

- 1) The frequencies of T and NK cell subsets will be analyzed by flow cytometry using antibodies for CD3, CD4, CD8, CD11b, CD11c, CD14, CD16, CD19, CD25, CD56,

and FoxP3. Special attention will be paid to CD8 T cell:CD4 Treg and NK:CD4 Treg cell ratios. We hypothesize that increased effector (CD8 and NK cell subsets versus Treg subsets) following pembrolizumab administration will be a biomarker positively associated with responsiveness to treatment and other major prognostic indicators for survival.

2) Activation and differentiation of T cell subsets will be analyzed by flow cytometry using additional antibodies for HLA- DR, CD38, CD57, CCR7, CD45RA and CD45RO. We hypothesize that activation and differentiation toward effector and memory responses versus exhaustion following pembrolizumab administration will be a biomarker positively associated with responsiveness to treatment and other major prognostic indicators for survival.

3) Immune cell functionality before and after pembrolizumab will be analyzed by assessing intracellular cytokines and effector molecules in serum via Luminex Multiplex Analysis against a panel of 48 human cytokines/chemokines. We hypothesize that increased expression of immune-stimulatory cytokines and effector molecules (versus inhibitory cytokines) following pembrolizumab administration will be a biomarker positively associated with responsiveness to treatment and other major prognostic indicators for survival.

4) Expression of the T cell inhibitory molecules PD-1, TIM-3, 2B4, Lag-3, and CTLA-4 on CD8+ T cells and their ligands (PD-L2, Gal9, CD48, CD80, CD86) will be evaluated on antigen presenting cells (MHC-II+) and tumor cells (CD45-) using respective monoclonal antibodies to these molecules and analyzed by flow cytometry. PD-L1 will be assessed from formalin-fixed paraffin-embedded by immunohistochemistry via Qualtek/Dako assay (Carpinteria, CA). We hypothesize that reduced expression of other T cell co-inhibitory molecules will be seen following pembrolizumab administration.

If samples are available, some or all of the following analyses may also be performed: nanostring, single cell RNA-sequencing, exosome sequencing, multispecial immunostain, proteomics and grafting of fresh tissue into experimental animals using blood and tumor tissue. The experimental protocol will follow laboratory SOPs and published procedures.

Leftover research specimens will be stored for future research for subjects who have provided permission.

